5.8.1 Participant Commitment	Approximately 16 weeks. This includes the two 8-week nutritional intervention periods (Mediterranean Diet and control diet).
5.8.2 Project Duration	The project will commence as soon as ethics has been approved, and the proposed project conclusion date is December 31 st , 2020.
5.8.3 Participant Follow up	Not applicable.
5.8.4 Discontinuation criteria	Participants may be discontinued from participating in the case that they enrol meeting inclusion criteria; however, their circumstances change to meet exclusion criterion during participation. For example, a participant requiring antibiotic medication during their participation will be discontinued as this medication can exert an independent influence on the gut microbiota.

5.9 Biological Sample Collection

5.9.1 What will be sampled and how?

Blood will be collected via IV catheterisation. Participants will rest in a supine position while a flexible 20-gauge Teflon catheter is inserted into an antecubital vein and attached to a three-way stopcock. This will allow for repetitive blood sampling during the oral glucose tolerance test (OGTT). The catheter will be kept patent by flushing it with isotonic saline after collection of each blood sample. Venous blood will be collected in EDTA, lithium heparin and serum-separating vacutainers. Blood samples will be collected on 3 clinical sessions. In the initial (baseline) clinical session and at a clinical session which immediately follows each of the 8-week dietary intervention periods (Mediterranean and control diet).

Oral Glucose Tolerance Test (OGTT): During each of the three clinical sessions, blood will be collected 4 times. A 20ml sample will be taken prior to glucose ingestion, and 20ml samples will be taken at 3 time points post ingestion (at 30 minutes, 60 minutes and 120 minutes). Thus, the maximum amount of blood taken per OGTT will be 80ml, with a total of 240ml taken throughout the research project. This compares with 500ml that is withdrawn during a standard donation at the blood bank.

Stool samples: Stool samples will be collected by participants. Participants will be provided with a stool collection kit (DNA Genotek OMNIgene-GUT Stool kit: <https://www.dnagenotek.com/us/products/collection-microbiome/omnigene-gut/OMR-200.html>) and related material. This includes a toilet collection hat, disposable gloves, collections spoons, a leak-proof primary receptacle with screw cap, leak-proof secondary receptacle with absorbent material and screw cap, padded envelope marked for mailing biological material and instructions for collecting/ mailing the specimen. An infographic of how

to collect the sample (Appendix I (ii)) and a short questionnaire about the collection time and date will be included in the collection kit.

Stool samples will be collected at three time points: within a week of the initial (baseline) clinical session, and at the end of each 8-week nutrition intervention (Mediterranean and control).

Buccal Swab/DNA Collection: Cells from inside of a person's cheek will be collected using a standard buccal swab at the baseline clinical session. Two swabs will be taken. This is a relatively non-invasive way to collect DNA samples and is not a certifiable activity. Each swab will be used for genetic profiling using Single Nucleotide Polymorphism arrays as per manufactures instructions. Genetic data collected will be coded. Participants will be advised that their material and data will not be released for such uses without their consent, unless required by law (as per the National Statement section 3.5).

5.9.2 Impact of and response to participant withdrawal

Participants have the right to withdraw at any time during the project, and the researchers will respect their decision. Participants will be informed of their right to withdraw their consent for their data to be used in the study, including time limitations to this (i.e. no data can be withdrawn following publication). Participants may withdraw at any time by informing a member of the researcher team by phone or email.

5.10 Data Management – Sample storage and disposal

Bio-specimens:

Plasma and serum samples will be decanted and aliquoted into de-identifiable labelled tubes, snap frozen in liquid nitrogen, and stored in a -80°C freezer for subsequent analysis.

Stool samples can be stored by participants in a provided biohazard mailing bag at room temperature until being mailed (or alternatively brought with them to their clinical session). It is recommended samples are sent to researchers immediately where possible. On arrival to the laboratory samples will be stored in a -80 °C freezer for subsequent analysis.

DNA samples will be stored in the freezer at (-20°C). Genetic data collected will be coded in a re-identifiable manner. Participants will be advised that their material and data will not be released without their consent, unless required by law (as per the National Statement 3.3). Additional information on genetic testing, to be supplied to participants as per Section 3.5.12 of the National Statement, will be provided in the Information to Participants form (Appendix B).

Blood and DNA samples will be taken by [name] and PhD student [name]. Stool samples will be collected by participants. [name] and [name] are qualified in IV Cannulation and Phlebotomy (qualification attached in Appendix G). DNA sample collection using buccal swabs is not a certifiable procedure. Participants do not require qualifications for stool collection. Participants will receive instructions for collecting/mailing the stool specimen, and additional verbal guidance of the process will be provided by researchers prior to collection.

Human bio-specimens will be coded and stored in RMIT Laboratories (in which security assess is required). Once the analysis has been conducted on the samples they will be destroyed. The analytical data attained from these samples will be retained for at least seven years.

Paper and electronic data:

A paper-based personal information and medical questionnaire (Appendix B) will be completed by participants at the baseline clinical session. Paper-based food records will be kept by participants prior to, and twice throughout the dietary intervention. All hardcopy records will be kept in a locked filing cabinet at RMIT.

Direct electronic data entry will be used when collecting biochemical, DEXA and respiratory gas measurements at clinical sessions. Direct electronic data entries, in addition to electronic data generated via experimental techniques (e.g. GC-MS chromatogram outputs for metabolomics and dietary analysis outputs via Foodworks Software), will be kept in password protect files on the RMIT desktops of the project investigators.

The scientifically validated Australian Eating Survey is a 120-item questionnaire which will be completed by participants online and password protected. The data export is available upon request by investigators at conclusion of the study by emailing [contact]. Data will be provided as a SPSS file for Windows Version 24 software. This data is compared to the Nutrient Reference Values and endorsed by the National Health and Medical Research Council. These outputs will be kept in password protect files on the RMIT desktops of the project investigators.

[name] will be responsible for the security of confidential data. All hardcopy data will be kept in a locked cabinet file at RMIT. All electronic data will be kept in password locked protected files on RMIT host servers. This data will be held for 15 years following publication (clinical trials data).

5.11 Data Analysis (including accounting for confounding factors and statistical power calculations)

Multivariate data attained through metabolomic techniques will be analysed as per statistical methods described by Danaher et al. (2016). Univariate data will be analysed using SPSS for Windows Version 24 software. Differences between allelic variant / genotype groups and individual metabolites, microRNA and gut microbiota will be examined using unpaired repeated-measures two-way ANOVA's. Where univariate analysis reveals any significant main effects for time, subsequent pairwise comparisons will be performed to detect differences over time. Where a genotype by time interaction is detected, multiple comparisons with Tukey's post hoc tests will be completed to identify differences. One-way ANOVA's will be performed for participant characteristic and indirect calorimetry data, with unpaired t-tests completed if interactions between factors are found. Linear regression and covariant analysis (ANCOVA) will be used to determine the effect of potential covariants (confounding factors) on allelic representation of dependent variables. Data will be expressed as mean ± SEM unless otherwise stated. The level of probability will be set at $p < 0.05$. Overall power of the data set will also be assessed via partial eta-square.

5.12 Data Linkage	Participants will be de-identified and assigned a code by the researcher. They will only be re-identifiable by the researcher to minimise privacy breaches. The re-identification is also important in the context of returning genomic research findings as per 3.3.58 of the National Statement. Data will not be linked to any public medical records.
5.13 Outcome measures	The main outcomes to be measured involve revealing if the genetic background of individuals affects their response to a Mediterranean diet by measurement of key physiological factors, including: 
 - Blood metabolites associated with glucose, fat and protein metabolism

	
 - Gene expression - Gut bacteria diversity and composition - Circulating hormones (ghrelin and insulin) 
Secondary outcomes that will also be measured include:
 
 - Body composition - Glucose tolerance - Food frequency and nutrient intake - Mood State

5.14 Will participants in the study be requested to modify any other treatments or interventions they may be receiving?
 
NO
	

5.15 Will participants in the study be requested to modify their regular daily activities (e.g. dietary intake, sleep, exercise)?
 
YES
 
If YES, provide details:
 
The participants will be modifying their regular dietary intake as described in sections 4.3 and 5.3.
	

5.16 Are any medication(s)/treatment(s) not permitted before and/or during the trial?
 
YES
 
If YES, provide details:
 
Volunteers taking contraindicated prescription medication (e.g. antibiotics, thyroid, hyperlipidemic, hypoglycemic, hypertensives, psychotropic drugs or appetite suppressants) will be excluded from participating (or have their participation discontinued) as these medications may exert an independent influence on microbiome, metabolic, anthropometric, biochemical, clinical and/or dietary outcomes monitored throughout the intervention.
	

5.17 Procedures for monitoring compliance
	
Participants will receive weekly support-orientated phone calls to ensure that procedures are being followed and how they are tolerating the intervention.
 
To monitor compliance to the dietary protocol, validated questionnaires will be used as described in section 5.8.

5.18 Are there any likely or expected negative side-effects of the intervention?
 
NO
	

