3.0 Resources	
3.1 Trial site	
RMIT University Bundoora West Campus
 
[name]
 
[name]
 
Ph: [name]

3.2 Resources necessary for the project to be conducted	
Clinical testing and data collection will be performed at the RMIT Bundoora Campus Clinical Suites (Building 203). This facility includes dual-energy x-ray absorptiometry (DEXA) equipment for body composition measurements, and will be made available to the researchers by RMIT.

	
Storage and experimental analysis of collected specimens will occur at the RMIT Bundoora Campus Biosciences Laboratories (Building 223). This will include the facilitation of measurement of metabolites (metabolomics) associated with glucose, fat and protein metabolism using gas chromatography-mass spectrophotometry.
 
The laboratory/premises and equipment to be used in this research have been subjected to OHS assessments and are deemed safe for use. Relevant risk assessments will be undertaken, and standard operating procedures will be generated, prior to experimental procedures in accordance with RMIT OHS requirements.
 
Additional resources/equipment that will be used for the project include:
 
 - Blood sampling items (including syringes, needles, adhesives, cleaning swabs and blood collection tubes) - Oral glucose tolerance testing drinks - Hormone (ghrelin and insulin) kits - Gene expression analysis (including extraction chemicals, microarray kits, real-time-PCR consumables) - Gut bacteria analysis (including faecal sample collection kits, extraction chemicals, 16S rRNA profiling and metagenomics consumables) - Genetic variant testing (including buccal swabs, extraction chemical, 10 x gene variant kits and associated consumables) - Food scales - Food frequency questionnaire access - Food hampers of example food products recommended throughout the dietary intervention.

3.3 Funding support
	
Funding to the value of \$129,287.13 (AUD) has been obtained from the Allen Foundation Inc for this research project (May 31st 2018 – May 31st 2021)
 
This philanthropic grant is subject to reporting of annual progress reports (due on May 31st over the three-year funding period).

3.4 Is the research of intervention sponsored?
 
NO
 
If YES, provide details of the sponsorship and any contractual or financial agreements entered into by the researchers:
 
Not applicable
	

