- (ii) Determine the potential of key genetic variants related to metabolic disease (including the Fat Mass and Obesity-Associated (FTO) gene, Transcription Factor 7-Like 2 (TCF7L2) gene, and Apolipoprotein E (APOE) gene) to influence gut bacteria, blood metabolite and gene modifying outcomes in response to the dietary interventions.
- (iii) Determine whether differences between genetic variants exist for body composition, key hormones (ghrelin and insulin), glucose tolerance, and dietary intake (food frequency and nutrient composition) in response to the dietary interventions.

It is hypothesized that variations in key genes associated with metabolic disease impacts on gut bacteria, blood metabolites and gene modifiers following an 8-week Mediterranean dietary intervention.

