4.8 Please describe the expected outcomes of this project

Primary Outcomes:

This study will reveal if the genetic background of individuals affects their response to a Mediterranean diet by measurement of key physiological factors, including:

- Plasma metabolites associated with glucose, fat and protein metabolism
- Gene expression
- Gut bacteria diversity and composition
- Circulating hormones (ghrelin and insulin)

Secondary Outcomes:

- Body composition
- Glucose tolerance
- Food frequency and nutrient intake
- Mood state

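### Section 5.11 sets one flat p < 0.05 for feature-by-feature genotype tests in at least three genes, with no stated control across features, outcome families or genes

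*Protocol*

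**What the plan says.** Section 5.11 (Data Analysis) fixes the unit of testing: "Differences between allelic variant / genotype groups and individual metabolites, microRNA and gut microbiota will be examined using unpaired repeated-measures two-way ANOVA's". It then gives a single level: "The level of probability will be set at" p < 0.05. No family-wise or false discovery level appears beside it.

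Two follow-up steps are described. For the interaction: "Where a genotype by time interaction is detected, multiple comparisons with Tukey's post hoc tests will be completed to identify differences". For time: "Where univariate analysis reveals any significant main effects for time, subsequent pairwise comparisons will be performed to detect differences over time"; no adjustment is named for these pairwise comparisons. Multivariate metabolomic data are sent to a cited method.

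Sections 4.8 and 5.13 list four primary or main outcome families without ranking them: metabolites (in 4.8, "Plasma metabolites associated with glucose, fat and protein metabolism"), gene expression, gut bacteria, and the hormones ghrelin and insulin. Aim (ii) in section 4.7 names three genes (FTO, TCF7L2, APOE) as examples rather than as a closed list. Sections 3.2 and 5.8 show that the platforms yield many features: microarray for microRNA, 16S rRNA profiling and metagenomics for stool, GC-MS for metabolites.

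**The concern.** The plan screens many features one at a time, repeats this for several genes, and calls each result at 5%. Tukey does not help with that screen. It starts only after an interaction has passed p < 0.05, and it compares group and time means for that one feature. Nothing stated limits the number of features, families or genes that pass by chance.

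Section 4.6 says that the results are meant to point to genetic sub-groups that may benefit from particular dietary advice. With four unranked primary families and no correction, a chance hit on any feature, in any family, for any gene could be reported as a positive primary result. A reader could not tell it from a real one.

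**Working it through.** **Inputs from the protocol**
- Level per test: 0.05 (5.11).
- Primary outcome families: 4, unranked (4.8, 5.13).
- Named genes: at least 3 (4.7, aim ii).
- Number of features per platform: not stated, so assumed below and shown as a range.

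The protocol gives no overall error rate, so there is no figure of its own to reproduce. The sample size of 120 does not enter the error calculation.

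**Step 1. Smallest count the protocol supports.** One test per family and gene: 4 × 3 = 12 tests. With independent tests and all nulls true, the chance of at least one false positive is 1 − (1 − 0.05)^m:
- m = 12: 1 − 0.95^12 = 0.460.

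**Step 2. Where 95% is reached.**
- m = 59: 1 − 0.95^59 = 0.952.
- 20 features in each of 3 genes is m = 60: 1 − 0.95^60 = 0.954.

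**Step 3. Allowing for correlation.** Features from one platform, and tests in the same participants, are correlated. For m two-sided normal tests with common correlation ρ, c = 1.96 and shared factor Z, the chance is 1 − E[{Φ((c − √ρ·Z)/√(1 − ρ)) − Φ((−c − √ρ·Z)/√(1 − ρ))}^m]:

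| Tests m | ρ = 0 | ρ = 0.3 | ρ = 0.5 | ρ = 0.8 |
|---|---|---|---|---|
| 12 | 46% | 40% | 32% | 19% |
| 60 | 95% | 85% | 66% | 31% |
| 300 | >99.9% | 99.9% | 95% | 46% |

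**Step 4. Expected number of false positives.** With all nulls true this is 0.05 × m, whatever the correlation:
- assumed 20 features × 3 genes = 60 tests: 3;
- assumed 100 features × 3 genes = 300 tests: 15;
- assumed 1,000 features × 3 genes = 3,000 tests: 150.

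**Step 5. Price of correction.** Take an assumed standardised difference of 0.5 between two equal genotype groups of 60. Power is 78% at 0.05, 60% at 0.05/4 = 0.0125, 45% at 0.05/12 = 0.0042 and 27% at 0.05/60 = 0.00083. These are Bonferroni levels, used only as an illustration; false discovery rate control would normally cost less.

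**The case against.** The strongest reply is that adjustment across features is commonly left to an SAP, that none is at hand, and that p < 0.05 does not itself say unadjusted. The cited multivariate method might also carry its own error control. Part of this stands: what the cited method does cannot be checked. But the protocol assigns that method to the multivariate metabolomic data, not to the univariate tests. For the univariate tests it states both the feature-wise unit and one level, and the only multiplicity device that it names acts within a feature. The finding rests on that stated rule, not on silence.

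A second reply is that the work is largely hypothesis-generating. Section 4.6 calls the findings a foundation for evaluating genomic screening, and section 7.1 returns genetic results with a caution that more research is needed. That softens the consequences, and it would go too far to say that a significant result carries no evidential weight. It does not make the flat level suitable for outcomes listed as primary.

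Several stronger readings are tempting but not supported:
- **False hits are near certain.** This depends on feature counts that the protocol does not give, and very strong correlation lowers the probability.
- **Ten variants, so 40 tests and 1 − 0.95^40 = 87%.** The resources list has "10 x gene variant kits", which may count kits rather than variants. No section says that ten variants will be tested.
- **Every primary family is screened feature by feature.** The ANOVA sentence covers metabolites, microRNA and gut microbiota. The two hormones fall only under the general level.
- **The outcomes are co-primary.** The protocol does not use that term. It often means that all must succeed, which would not inflate error.
- **The hormones have contradictory tiers.** Aim (iii) groups "body composition, key hormones (ghrelin and insulin), glucose tolerance" with other measures, and the hypothesis omits hormones. But section 4.7 ranks no aims, and 4.8 and 5.13 agree that hormones are primary. The wording is untidy, not contradictory.

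**Conclusion.** The point holds. Followed as written, section 5.11 gives no control of false positives across features, primary families or genes.

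The figure that rests only on counts in the protocol is 46% for 12 tests, assuming independence and all nulls true; it falls to 40% at correlation 0.3 and 32% at 0.5. At feature level the size is conditional. An assumed 100 features in 3 genes gives 15 expected false positives, and about 59 independent tests are enough for a 95% chance of at least one. Microarray, 16S or metagenomic and GC-MS data in three genes would plausibly exceed 59 tests, but that is an inference, not a count in the document.

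**What to change.** In section 5.11, replace the flat threshold with the following:
- **Omics tests.** For the feature-wise genotype tests, taken as the genotype-by-time interaction that the plan states, apply a Benjamini-Hochberg false discovery rate of 5% within each of the metabolite, microRNA and gut microbiota families, over all features × genes tested.
- **Hormones.** Apply Holm to the ghrelin and insulin tests across genes. With three genes that is 2 × 3 = 6 tests, so the smallest p-value is compared with 0.05/6 = 0.0083.
- **Everything else.** Report as exploratory, with 95% confidence intervals.
- **Scope of control.** State that error is controlled within each of the four families and not across them. With all nulls true and independent families, four separate 5% budgets leave 1 − 0.95^4 = 18.5%, so a hit in one family must not be presented as overall trial success.

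This needs wording and a standard analysis step; it needs no new participants, samples or visits. The cost is that fewer features will be called significant and per-feature power falls. The 80% power statement in section 5.4 should therefore be described as applying to a single test at 0.05. The rule should be fixed before the data are seen.

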5.0 Project Design

5.1 Research Project Setting	The clinical sessions will be undertaken at the RMIT Bundoora Campus Clinical Suites (Building 203).
-------------------------------------	--

5.2 Trial design	The study will use a randomised, controlled, cross-over design.
-------------------------	---

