5.4 Population to be studied

Description and number:

This trial will recruit n = 120 healthy males and females aged between 18 - 55 years who are deemed eligible to participate as indicated by not meeting one or more of the exclusion criterion (see section below). For withdrawal of subjects see section 5.9.2.

Inclusion criteria:

Individuals with a body mass index greater than 18.5 kg/m², males and females aged between 18 - 55 years who are deemed eligible to participate as indicated by not meeting one or more of the exclusion criterion.

Exclusion criteria:

Participants will be excluded from participating within the project for the following reasons: Individuals with presence of psychiatric disorders, pathologic eating disorders, chronic diseases related to the metabolism of energy and nutrients (i.e. hyperthyroidism), difficulty in changing food habits, participants with special dietary needs (e.g. exclusion of whole food groups), and/or unable or unwilling to give informed consent. These exclusion criterion are set as they may influence an individual's ability to comply with the recommendations of the nutritional intervention.

Additional exclusion criterion includes: weight instable in the previous 3 months (evident by a loss or gain of more than 10% of total body weight), pregnant or potentially pregnant, post-menopausal, taking contraindicated medication (e.g. antibiotics, thyroid, hyperlipidemic, hypoglycemic, hypertensives, psychotropic drugs or appetite suppressants) or the use of any dietary supplement that might interfere with the results of the study. These additional exclusion criteria are set as they may exert an independent influence on microbiome and metabolic outcomes, anthropometric, biochemical, clinical, body composition (DEXA) analysis and/or dietary outcomes monitored throughout the intervention.

Sample size and statistical or power issues

Statistical power for a sample size of at least 120 participants to detect a medium effect size with 80% power was calculated upon previously published data on cross-over (Itsiopoulos et al. 2011 (n=27); Ryan et al. 2013 (n=12)) and single arm studies (Di Renzo et al. 2018 (n=188, split on FTO genotype); Jacka et al. 2017 (n=67); Papamiltiadous et al.

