	
2016 (n=94); Parletta et al. 2007 (n=152)). In these studies, a 6 week to 3-month Mediterranean diet - control intervention was able to have a significant influence on a variety of physiological and psychological outcomes. Based on allowances for attrition, including predicted dropout rates, sample size was inflated by 20% for the current project (to n=120 overall), which takes a randomised cross over approach and accounts for genotypic influences on data outcomes.

5.5 Participant recruitment strategies and timeframes
	
Volunteers will be recruited from the RMIT University staff and student population, and also the local community (surrounding Melbourne Suburbs) by word of mouth and electronic (i.e. RMIT Facebook and Twitter) (Appendix F iii) and print advertisement (i.e. flyers) (Appendix F ii). Researcher contact details (phone and email) will be provided on electronic and print advertisement material.
 
Volunteers willing to participate in the study will be provided with a NHMRC 'Information to participants' form approved by RMIT HREC (Appendix B). This will be provided through email or mail based on volunteer preference. Volunteers will have the opportunity to receive further information over the telephone, email and/or face-to-face.
 
The principle research student [name], and Chief Investigator ([name]) will be the primary contacts for potential participants. Individuals expressing interest in participating in this study will be initially interviewed/screened over the phone or in person to determine suitability to participate in this study (please refer to section 5.4 for the inclusion and exclusion criteria). Participants believed to meet eligibility criteria will be invited to attend a familiarization session (section 5.6). (See Appendix F (iv) for an example of email correspondence).
 
Volunteers will be given time to think about participation (i.e. talk to family or friends) and they can consider participation during the time the study runs (i.e. there is no set timeframe). Volunteers willing to participate in the study will be asked to sign an Informed Consent form and reminded that participation is completely voluntary, and that they can withdraw from the study at any time.

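### Section 5.11 names partial eta-squared as the measure of the data set's power, but it is an observed effect size and cannot show whether a null genotype result is informative

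*Protocol*

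**What the plan says.** The heading of section 5.11 promises both data analysis and power calculations. After listing the univariate tests, it closes with: "Overall power of the data set will also be assessed via partial eta-square". The section names no other measure of power.

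The main univariate analyses compare genotype groups on metabolites, microRNA and gut microbiota. These "will be examined using unpaired repeated-measures two-way ANOVA's", with post hoc tests where a genotype-by-time interaction appears. The significance level is 0.05. Sections 5.3 and 5.9.1 give three clinical sessions: baseline and the end of each diet period.

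Prospective power is handled elsewhere. Section 5.4 refers to "Statistical power for a sample size of at least 120 participants to detect a medium effect size with 80% power" and adds that the "sample size was inflated by 20% for the current project (to n=120 overall"). It does not mention partial eta-squared.

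**The concern.** Power is the probability that a test detects a specified effect at a given sample size and alpha. Partial eta-squared describes how large an effect looked in the data obtained. Section 5.11 puts the second in place of the first.

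The main question is whether genotype modifies the response to the diet, examined over many metabolites, microRNAs and bacterial measures, so some null results should be expected. For each, a reader will want to know whether a worthwhile difference has been ruled out or the data were too sparse to say. Section 5.4 helps little after the fact, because it gives no endpoint, standard deviation or numerical effect. If partial eta-squared is then offered as power, the question appears answered when it is not.

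**Working it through.** **The plan's own figure.** The sentence in section 5.11 gives no number, so there is none to reproduce. The 80% in section 5.4 belongs to a separate calculation. It cannot be uniquely reproduced, because the effect is described only as medium and the test is not named.

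The sentence can be read in two ways, and each was checked.

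**Reading 1: partial eta-squared itself indicates power.**

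Inputs: alpha 0.05 (section 5.11). A two-group F test and Cohen's f = 0.25 are assumed for illustration, since the protocol gives no numerical effect.

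- Conversion: partial eta-squared = f²/(1 + f²) = 0.0625/1.0625 = 0.059.
- Power: the probability that a noncentral F variable with 1 and N − 2 degrees of freedom and noncentrality N × f² exceeds the 5% critical value.
- Observed F for this partial eta-squared: F = (N − 2) × f².

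| N | Noncentrality (N × 0.0625) | Critical F | Power | p if 0.059 is observed |
|---|---|---|---|---|
| 20 | 1.25 | 4.41 | 18.5% | 0.30 |
| 50 | 3.125 | 4.04 | 41% | 0.09 |
| 100 | 6.25 | 3.94 | 70% | 0.015 |
| 120 | 7.5 | 3.92 | 77.5% | 0.008 |
| 200 | 12.5 | 3.89 | 94% | not needed |

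The same partial eta-squared goes with power from 18.5% to 94%, so the value alone says nothing about power.

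**Reading 2: power is computed afterwards from partial eta-squared.**

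- Partial eta-squared = F × df1/(F × df1 + df2). With df1 and df2 fixed, it is a one-to-one function of F, and so of p.
- Observed power is the noncentral F probability above the 5% critical value, with noncentrality df1 × F.

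With 1 numerator degree of freedom and p exactly 0.05:

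| N | Partial eta-squared | Observed power |
|---|---|---|
| 20 | 0.197 | 51.1% |
| 50 | 0.078 | 50.4% |
| 100 | 0.039 | 50.2% |
| 120 | 0.032 | 50.2% |

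A sixfold change in sample size leaves observed power at about one half, because it is tracking p.

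A genotype-by-time interaction over three visits has (groups − 1) × (3 − 1) numerator degrees of freedom: 2 with two genotype groups and 4 with three. Taking N = 100 as an assumption, the error degrees of freedom are (100 − 2) × 2 = 196 and (100 − 3) × 2 = 194, with no sphericity correction.

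| Test | p | F | Partial eta-squared | Observed power |
|---|---|---|---|---|
| F(1, 98) | 0.05 | 3.94 | 0.039 | 50% |
| F(1, 98) | 0.20 | 1.67 | 0.017 | 25% |
| F(2, 196) | 0.05 | 3.04 | 0.030 | 58% |
| F(2, 196) | 0.20 | 1.62 | 0.016 | 34% |
| F(4, 194) | 0.05 | 2.42 | 0.048 | 69% |
| F(4, 194) | 0.20 | 1.51 | 0.030 | 46% |

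Within each test, knowing p gives both other columns. Neither adds information about the sensitivity of the design.

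**The case against.** The strongest reply is that this is one loosely worded sentence on which nothing depends. Sample size is set in section 5.4 without partial eta-squared, and the alpha and the tests stand as they are. Reporting partial eta-squared beside an ANOVA is unobjectionable. That is correct, and it is why severity is low. It does not rescue the sentence, which assigns the quantity a meaning it does not have. This is a positive statement, not a detail left to a later analysis plan.

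A reader might infer more than the protocol supports:

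- **That the sample size of 120 is undermined.** It is not. The power statement in section 5.4 is separate.
- **That null genotype results will be explained away as underpowered.** Section 5.11 does not say so, nor does it say that observed power will be calculated. Reading 2 is one possible meaning.
- **That a non-significant result must show 50% power or less.** That is roughly true only with 1 numerator degree of freedom. With 2 or 4, a result just short of significance shows up to about 58% or 69%.
- **That partial eta-squared ignores the within-person comparison.** In a repeated-measures ANOVA, its value for time or genotype-by-time uses the within-subject error term. How diet enters a model that names genotype and time is a separate question.
- **That the default of mean ± SEM belongs to the same error.** The text reads "Data will be expressed as mean ± SEM unless otherwise stated". It is a display default with room for exceptions, changes no test, and can be settled in an analysis plan that is not shown. The protocol does not mention error bars.

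**Conclusion.** The point holds for the power sentence only. Partial eta-squared is an effect size. As a direct index of power it is uninformative, since 0.059 goes with anything from about 18% to 94% as N runs from 20 to 200. As the basis for power computed afterwards it repeats the p-value: about 50%, 58% or 69% at p=0.05 with 1, 2 or 4 numerator degrees of freedom. It therefore cannot show whether a null genotype result is informative.

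The general conclusion follows from the definitions. The figures rest on assumptions that the protocol does not supply: f = 0.25, two or three genotype groups, N = 100 for the interaction tests, and unadjusted degrees of freedom. Severity is low, because no sample size, alpha level or test changes.

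**What to change.** In section 5.11, delete the sentence on power, or reword it so that partial eta-squared is reported as an effect size only. Add that the diet and genotype-by-diet effects will be given as model-estimated differences with 95% confidence intervals, and that the informativeness of a null result will be judged from whether the interval excludes differences of interest.

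The cost is one or two sentences. It needs no new data or visits and no change to sample size, alpha or tests.
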